## 12. STATISTICAL ANALYSIS

- *Describe how your data will be used to test the hypotheses.*
- *State clearly what variables will be tested and what statistical tests will be used.*
- *Include sample size calculations.*
- *If this is a pilot study, state which variables will be examined for hypothesis generation in later studies.*

Analysis for the Primary Aim: The minimum effective dose (MED) will be defined as the smallest BCT dose duration associated with a successful PA increase (defined as an average increase of 2,000 steps per day) between the 2-week run-in and 2-week follow-up periods in at least 80% of participants. The MED will be estimated based on the modified TiTE-CRM, which is an adaptive model-based, dose-finding design for estimating the maximum tolerated dose in pharmacologic agents. In this study, we will adapt the TiTE-CRM for the purpose of MED estimation. Briefly, the TiTE-CRM operates as follows during a study. Participants will be enrolled in cohorts of 3. The first cohort will be given a BCT intervention with a duration of 5 weeks. Subsequent cohorts will be given a BCT intervention duration (from 1-week to 10-week) based on the updated MED estimate according to the modified TiTE-CRM model and data from the previously enrolled participants. The process will continue until we reach a total of 42 participants (14 cohorts) randomized to the intervention. Once the study has completed enrollment, we will identify which dose of the BCT intervention (in weeks) is associated with  $\geq 80\%$  of participants achieving the goal of an average of 2,000 steps per day increase between the baseline and follow-up periods. Means and standard deviations of step scores for baseline versus behavioral change strategy treatment period will be visualized using a column graph. The statistical significance of differences will be adjusted for time interval. The effects of treatment on number of steps will be assessed using generalized linear mixed models (GLMM). This model will account for possible autocorrelation and linear trends between steps across time.

Analysis for Secondary Aim 1: To identify estimates of the indirect effect of the BCT intervention on PA via potential mediator MoAs, we will conduct the analysis in 3 steps using mixed effects regression models. First, we will estimate the direct effect of the BCT intervention on PA. Second, we will estimate the effect of the BCT intervention on each potential MoA. Third, we will estimate the indirect effect of the BCT intervention on PA.

Analysis for Secondary Aim 2: The effect of the multi-BCT intervention on adherence to statins will be examined across the study duration. Participant steps will be assessed continuously using a Fitbit mobile device. Daily steps for participants will be aggregated by run-in and follow-up periods to generate average daily steps in each period. Changes in daily steps between run-in and intervention periods will be compared using Generalized Linear Mixed Model Analyses.

Analysis for Exploratory Aim: Participant heterogeneity in amount of time required to reach a successful increase in daily steps (defined as an increase of 2,000 or more steps per day over a 2-week period compared to run-in) will be examined. Average step counts will be calculated for each 2-week block during the intervention and follow-up periods. Average steps per day in these blocks will be compared with the average daily steps in the run-in period. Once a successful increase has been detected, the time to achieve this treatment response will be recorded. Differences in duration

to successful increases in physical activity will be examined between participants using mixed effects regression models.

The sample size of 42 participants randomized was chosen to have a sufficient number of participants to obtain a preliminary assessment of the MED for the five-component behavioral change intervention to increase walking between baseline and follow-up periods. The duration of dose and number of measurements/reports were based on expert recommendations and estimations about maximal duration of the trial to maintain patient engagement. Data will be reported transparently so that individual level heterogeneity can be assessed.

The dose-efficacy model is calibrated such as that the modified TiTE-CRM will eventually select a BCT duration associated with 75%-85% successful PA success, i.e., within 5 percentage points of our target [30]. The sample size (n=42) is determined to achieve 60% probability of correct selection (PCS) under logistic dose-efficacy curves with slope = 0.69 (i.e., an OR = 2) [31]. As this is small-scale pilot study, power and sample size will be calculated solely for the primary aim.

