The sample will include individuals prescribed primary prevention statin therapy with self-reported low levels of physical activity. Participants will complete a 2-week baseline run-in period where PA levels will be measured using Fitbit wearable devices and levels of adherence to statin medications will be assessed using eCAP smart pill bottles. During the baseline period, data from the Fitbit wearable devices will be used to verify participant's level of objective sedentary behavior. Individuals who are non-adherent to the protocol will be excluded and will not be randomized to the intervention. Following baseline, we will randomize 42 participants into 14 cohorts of 3 participants each for the intervention period. During the intervention period, participants will receive a BCT intervention, the length of which varies between 1 and 10 weeks depending on the assigned dose of a multi-BCT intervention. Assignment to doses will utilize modified TiTE-CRM methodology to adjust the dose for each cohort based on the results from the previous cohort. Following the intervention, all participants will be assessed over a 2-week follow-up period which includes passive data collection from the activity monitor, answering surveys and use of eCAP smart pill bottles to track medication adherence.

All collected data will be stored in the REDCap program, which is a Northwell IRB and Research IT security approved application, housed on the Northwell IT approved server. The MED will be defined as the smallest BCT dose duration associated with 80% of participants having a successful PA increase between the run-in and the follow-up periods. Change in PA will be defined as the difference in average daily PA between the run-in and follow-up periods. We will also assess Mechanisms of Action (MoAs) to determine potential mediators of the BCT intervention on PA. As increasing

PA may change statin adherence [7, 8], we will utilize eCAP smart pill bottles to measure adherence to statin medications.

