### 4. OBJECTIVE(S)/SPECIFIC AIMS AND HYPOTHESES

- *A concise statement of the goal(s) of the current study.*
- *The rationale for and specific objectives of the study.*
- *The goals and the hypothesis to be tested should be stated.*

The current study aims to identify the required dose of a behavioral change technique (BCT) intervention to increase physical activity (PA) by an average of 2,000 steps per day among individuals on primary prevention statin therapy with elevated risk for cardiovascular disease (CVD). The study will utilize the modified time-to-event continual reassessment method (TiTE-CRM).

**Primary Aim:** Identify the MED of a multi-BCT intervention required to increase PA by an average of 2,000 steps per day between run-in and follow-up periods in at least 80% of participants.

**Secondary Aim 1:** To identify effect sizes for mediating MoAs of the BCT intervention on PA.

**Secondary Aim 2:** Identify additional benefits of the BCT intervention on statin adherence.

**Exploratory Aim:** Identify between-person heterogeneity in Treatment Response.

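### The supporting step-count summary and comparison use the intervention period, whereas change in physical activity is defined by the message-free follow-up

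*Combined protocol and SAP*

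**What the plan says.** The definition of the outcome is consistent. Section 2 states: "Change in PA will be defined as the difference in average daily PA between the run-in and follow-up periods". The Primary Aim in section 4 is to "increase PA by an average of 2,000 steps per day between run-in and follow-up periods in at least 80% of participants". Section 12 defines the MED by a successful increase "between the 2-week run-in and 2-week follow-up periods in at least 80% of participants". Section 11 bases the dose for the next cohort on the same gain from baseline to follow-up, and says that nothing is delivered to participants during follow-up.

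The step analyses in section 12 name other windows.

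- Primary Aim, graph: "Means and standard deviations of step scores for baseline versus behavioral change strategy treatment period will be visualized using a column graph".
- Primary Aim, next sentence: "The statistical significance of differences will be adjusted for time interval". It names no periods of its own.
- Primary Aim, model: a generalized linear mixed model (GLMM) for the effect of treatment on step count, allowing for autocorrelation and linear trend. It names no periods either.
- Secondary Aim 2, aggregation: "Daily steps for participants will be aggregated by run-in and follow-up periods to generate average daily steps in each period".
- Secondary Aim 2, comparison, in the following sentence: "Changes in daily steps between run-in and intervention periods will be compared using Generalized Linear Mixed Model Analyses".

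**The concern.** The two windows measure different things. The intervention window records walking while five texts arrive each day, and its length is the assigned dose. The follow-up window records walking after the texts stop, and it lasts two weeks for everyone. Only the second defines success.

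A reader who sees a column graph and a model estimate beside the MED will take them as describing the outcome behind the MED. If activity falls when the texts stop, the reported mean gain will look better than the responder rate. If activity builds up over weeks and persists, the intervention mean will understate it, and by more at longer doses. In either case the step effect from this pilot would be a poor input for planning a later trial on the same endpoint. Leaving the window open also allows it to be chosen after the data are seen.

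**Working it through.** **Which periods each sentence compares**

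| Place | Use | Periods |
|---|---|---|
| Section 2 | definition of change in physical activity | run-in, follow-up |
| Section 4, Primary Aim | 2,000-step gain in at least 80% | run-in, follow-up |
| Section 11 | dose for the next cohort | baseline, follow-up |
| Section 12, Primary Aim | MED definition | run-in, follow-up |
| Section 12, Primary Aim | step means and SDs (graph) | baseline, treatment period |
| Section 12, Primary Aim | steps GLMM | not named |
| Section 12, Secondary Aim 2 | aggregation of steps | run-in, follow-up |
| Section 12, Secondary Aim 2 | steps GLMM | run-in, intervention |
| Section 12, Exploratory Aim | 2-week blocks, time to response | run-in against each block of intervention and follow-up |

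The only summary of step means and the only step model with named periods both use the intervention window. Follow-up against run-in is compared only through the responder proportion behind the MED and within the exploratory blocks. Follow-up averages are formed under Secondary Aim 2, but the comparison there does not use them.

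**Window lengths.** Intervention: 1 × 7 = 7 days to 10 × 7 = 70 days. Follow-up: 2 × 7 = 14 days for all.

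**The plan's own figure.** No figure is stated for the step contrast, so there is none to reproduce. The only design figure is n = 42 for a 60% probability of correct selection of the MED, which this point does not touch.

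**How far the contrasts can differ.** The step values below are assumed, because the documents give no step means or SDs.

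1. Gain partly lost. Run-in 5,000, intervention 8,000, follow-up 6,500 steps per day. Intervention minus run-in: 8,000 − 5,000 = 3,000. Follow-up minus run-in: 6,500 − 5,000 = 1,500. The first is above the 2,000-step threshold and the second is below it.

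2. Gain builds up and persists. Suppose a linear rise to 3,000 by week 10, which is 3,000 / 10 = 300 steps per day for each week. After w weeks the follow-up gain is 300w and the mean over the intervention is 300w / 2 = 150w. The shortfall is therefore 150w: 150 at 1 week, 750 at 5 weeks, 1,500 at 10 weeks. It depends on dose.

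3. Effect on responders. Assume that individual change is normal with standard deviation s, and set the on-message mean m so that 80% gain at least 2,000: m = 2,000 + 0.8416 × s. If a share q of the mean gain is kept at follow-up, the responder share is Φ((q × m − 2,000) / s).

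| s | m | q = 1 | q = 0.75 | q = 0.50 |
|---|---|---|---|---|
| 1,000 | 2,842 | 80% | 55% | 28% |
| 2,000 | 3,683 | 80% | 65% | 47% |
| 3,000 | 4,525 | 80% | 68% | 53% |

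For the first row at q = 0.75: 0.75 × 2,842 = 2,131, (2,131 − 2,000) / 1,000 = 0.131, and Φ(0.131) = 0.55. In this illustration, an on-message result that just meets the 80% target would miss it at follow-up unless the gain is fully kept.

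**The case against.** The strongest reply is that no decision in the trial uses the graph or the steps model. That is right. A reader might infer from the mismatch that the MED is estimated on the wrong outcome. The documents do not support this: sections 2, 4, 11 and 12 all tie success, dose assignment and the final MED to follow-up.

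A reader might also infer that every planned step model uses the wrong window. The GLMM under the Primary Aim names none, and its allowance for autocorrelation and trend suggests a model of the whole daily series. The explicit mismatch in a model is one sentence, and it sits under the statin-adherence aim, where it may be misplaced text.

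Nor are the two Secondary Aim 2 sentences impossible to carry out together. Steps are recorded continuously, so an intervention mean can be formed, or daily steps modelled directly. The sentences are mismatched, not mutually exclusive.

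Finally, a reader might infer that follow-up steps would never be set against run-in apart from the MED. The Exploratory Aim does this in fixed 2-week blocks, which also eases the unequal-window problem there. That analysis is aimed at time to response, however, so it does not supply the missing main contrast. The sentence on adjusting for time interval may be meant for unequal windows, but it does not say so, and it could not turn an on-message gain into an off-message one.

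What remains is that the named contrasts do not match the protocol's own definition of change. Loose wording is possible, but the protocol treats run-in, intervention and follow-up as separate phases, so the text needs correcting on either reading. An on-message contrast is legitimate, provided that it is labelled as such.

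**Conclusion.** Wrong as written, but minor and limited to the supporting step analysis. The MED definition, dose assignment and sample size stand. The textual finding rests on no assumption: the step comparisons with named periods use the intervention window, while change in physical activity is defined at follow-up. The size of the discrepancy cannot be derived from the documents. The illustrations show only that it can go in either direction and can cross the 2,000-step threshold. They do not show that it will. If the gain were constant from the first day of messages and fully kept afterwards, the two contrasts would agree.

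**What to change.** In section 12, Primary Aim, show step means and SDs for run-in, intervention and follow-up, pooled over durations. A split by duration would not work: 3 periods × 10 durations is up to 30 columns from 42 participants, or 42 / 10 = 4.2 per duration if spread evenly, and adaptive assignment will not spread them evenly. Note beside the intervention column that its window runs from 7 to 70 days.

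In the same paragraph, give the steps GLMM a three-level period factor, with follow-up minus run-in as the main contrast and intervention minus run-in as a labelled secondary, on-message contrast. If the linear time trend is kept, report each contrast as a difference between model-based period means, because the period coefficient alone would be net of the trend.

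In Secondary Aim 2, change the comparison to run-in versus follow-up, so that it matches the aggregation sentence before it.

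The cost is three edited sentences and a little more analysis and reporting. No further data, participants or procedures are needed.

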## 10. ENDPOINTS

- *Describe the primary and secondary study endpoints*
- *Describe any primary or secondary safety endpoints*

This study is a pilot whose primary purpose is to identify the MED of a multi-component BCT intervention needed to increase PA among participants on primary

prevention statin therapy. Secondary endpoints include pooling trial results across all participants to assess the mediation of MoAs for BCTs on physical activity and to identify any potential benefit of BCTs on increasing statin adherence.

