Potential participants will be first linked to an authorization form, allowing the study team to collect PHI necessary for the study. Participants who authorize PHI collection will then be asked to provide demographic information needed to comply with NIA reporting requirements. This basic demographic information (including age, sex, race, and ethnicity) will be used by the study sponsor for the purpose of determining equity and representativeness in recruitment for clinical trials. This demographic information is collected prior to eligibility screening to ensure that the study is not excluding potential participant groups. Afterwards, participants will be directed to an electronic screening questionnaire administered via REDCap to determine their eligibility. If eligible, participants will be automatically allowed to review and sign an informed consent form. Those who have signed the informed consent form are encouraged to discuss study procedures and address any questions with a clinical research coordinator. Prior to receiving study devices, participants will read and sign a device allocation document letting them know which devices they may keep upon study completion and which devices should be returned to study staff. Both eligible and ineligible participants will be presented with a series of optional demographic questions. Asking these questions is required by the study sponsor (NIA) with the intention of improving equity and representativeness in clinical trial recruitment. The optional questions are presented regardless of eligibility to ensure that the study is not excluding potential participant groups. These demographic questions will be provided to the NIA, the study sponsor, as part of the continuing report process. Study staff will set up the eCAP device and assign it to participants as they are enrolled and consented. Participants who sign consent will then be asked to answer some demographic questions during onboarding and will be mailed a commercially available Fitbit device and eCAP smart pill bottle after onboarding is complete. Upon receiving the smart pill bottle, participants will fill the eCAP pill bottle using their existing statin prescription.

The intervention will utilize the modified TiTE-CRM design as well as 5 BCTs, which

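### The Secondary Aim 2 analysis is meant for statin adherence, but the only measure, aggregation and model it specifies are for Fitbit steps

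*Combined protocol and SAP*

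**What the plan says.** Section 4 gives Secondary Aim 2 as "Identify additional benefits of the BCT intervention on statin adherence". Section 10 lists the matching secondary endpoint, which is "to identify any potential benefit of BCTs on increasing statin adherence". Section 2 names the instrument: "we will utilize eCAP smart pill bottles to measure adherence to statin medications". Section 11 adds that "participants will fill the eCAP pill bottle using their existing statin prescription". Section 14 (Medication Adherence) says that adherence is monitored daily, that the device records bottle openings, and that the data can be downloaded once the bottle has been returned.

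The analysis of this aim is one paragraph in section 12, with four sentences. The first is "The effect of the multi-BCT intervention on adherence to statins will be examined across the study duration". The second says that steps are recorded continuously by Fitbit. The third is "Daily steps for participants will be aggregated by run-in and follow-up periods to generate average daily steps in each period". The fourth is "Changes in daily steps between run-in and intervention periods will be compared using Generalized Linear Mixed Model Analyses".

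Earlier in section 12, under the Primary Aim, the plan already states: "The effects of treatment on number of steps will be assessed using generalized linear mixed models (GLMM)".

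**The concern.** The paragraph announces one outcome and then specifies the analysis of another. A statistician who programs what is written would fit a mixed model to step counts and report it under an aim about statin adherence. That model would give no adherence estimate.

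Adherence would then have to be analysed without a plan. The scoring of bottle openings, the periods compared and the treatment of days without data could all be settled after the eCAP data had been seen. The instructions at the head of section 12 ask for the tested variables and the tests to be stated clearly. For this aim, the variable stated is not the one in the objective.

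**Working it through.** No arithmetic applies beyond a count of sentences. The check compares what the aim needs with what the text supplies, and then looks for the missing parts elsewhere.

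**1. The Secondary Aim 2 paragraph, sentence by sentence.**

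| Sentence | Subject | What it fixes |
|---|---|---|
| 1 | Statin adherence | Intent only: no variable, contrast or model |
| 2 | Steps | Measure (Fitbit) |
| 3 | Steps | Aggregation (run-in and follow-up means) |
| 4 | Steps | Model (GLMM) and contrast (run-in, intervention) |

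Adherence is named in 1 of 4 sentences, without a method. Steps are the subject of 3 of 4, and these hold every operational detail. Neither the eCAP bottle nor bottle openings appear in the paragraph.

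**2. Is the missing part supplied elsewhere?** Sections 2, 11 and 14 supply the device. Section 14 also supplies the unit (daily) and the raw datum (openings). No section gives the rule that turns openings into an adherent or non-adherent day, a summary by period, the contrast, the model, or the handling of absent eCAP data. The other analyses in section 12 have these outcomes:
- Primary Aim: success on the 2,000-step criterion, and number of steps.
- Secondary Aim 1: physical activity and the mechanisms of action.
- Exploratory Aim: time to a successful step increase.

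None has adherence as its outcome.

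**3. Does the step model add anything where it stands?** The Primary Aim text already has a GLMM for the effect of treatment on steps, allowing for autocorrelation and linear trend. The GLMM under Secondary Aim 2 has the same outcome and model class, so it is largely a repeat.

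**4. Is the step text consistent with itself?** Sentence 3 averages steps over run-in and follow-up. Sentence 4 compares run-in with intervention. The aggregation produces no intervention-period mean for that comparison, and the follow-up mean it does produce is not used. Putting adherence in place of steps would therefore still leave the contrast undetermined.

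**The case against.** The strongest reply is that this is a drafting slip in a secondary aim of a self-described pilot. The first sentence does commit the study to examining adherence, the device is specified, and section 14 gives a daily unit and the raw datum. Section 12 limits the power and sample size calculation to the primary aim. All of that stands, and it bounds the point: what is absent is the scoring rule, contrast and model, not the measurement. It does not remove the point. Pilot status explains why there is no power calculation for this aim, but not why the stated model has a different outcome.

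Two stronger readings are tempting and are not supported.

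- A reader might infer that adherence will not be measured or analysed at all. Sections 2, 11 and 14 and the first sentence of the paragraph say otherwise.
- A reader might infer that the adherence analysis leaves out the intervention period, because sentence 3 covers only run-in and follow-up, and might then express the loss as a share of study days. That sentence concerns steps, the whole-study commitment concerns adherence, and sentence 4 does bring in the intervention period. A share of days computed this way would not measure the defect.

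It is also fair to say that no single adherence model is the only correct one. Daily yes/no adherence and the proportion of adherent days per period would both close the gap.

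**Conclusion.** The point holds, and the paragraph is wrong as written rather than merely short of detail: the only specified model under Secondary Aim 2 answers a question about steps. In size, it affects the whole specified analysis of one secondary aim and nothing else. The MED estimate, the assignment of durations to cohorts and the collection of eCAP data do not depend on it. It should be corrected, but it does not threaten the trial.

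The conclusion rests on reading the four sentences as they stand and on finding no adherence outcome or model in any other section. One related assumption matters for the fix. eCAP use is stated expressly for run-in and follow-up. For the intervention period it is inferred from the daily monitoring in section 14 and the whole-study commitment in section 12.

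**What to change.** Replace the three step sentences under Secondary Aim 2 with an eCAP-based adherence analysis, fixed before any adherence data are analysed. It need not be fixed before the first download, since bottles come back participant by participant over 14 cohorts. The text should state five things; the choices below are one workable example.

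- **Population:** participants who start the intervention. Up to 100 may enrol and 42 are to be randomised, so some people will have run-in data only.
- **Outcome:** each monitored day adherent or not, from bottle openings; alternatively, the proportion of adherent days per period. Say what dosing schedule is assumed. Bottles are filled from the existing prescription, but no section says that the prescribed schedule is recorded as study data, so either state an assumption or add that item.
- **Model:** logistic mixed model with a participant random effect and a fixed effect for period (run-in, intervention, follow-up), allowing for autocorrelation and time trend as the Primary Aim GLMM does. State the form of the trend in advance, because period and study day overlap within a participant.
- **Contrasts:** intervention versus run-in and follow-up versus run-in, described as before-after changes.
- **Missing data:** days without eCAP data (unreturned bottle, withdrawal) are missing, not non-adherent, and their number is reported.

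Delete the step sentences from this paragraph, or move them to the Primary Aim text and reconcile the periods there.

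The cost is a small amount of analysis wording and one stated dosing-schedule assumption. If the schedule is collected instead, one data item is added. Study procedures are otherwise unchanged.

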## 9. STUDY TIMELINES

- *Describe the duration of an individuals participation in the study*
- *Describe the duration anticipated to enroll all study subjects*
- *The estimated date of study completion*

Participants in this research could remain on study for up to 14 weeks.

All participants will undergo a 2 week run-in period and will then be enrolled in cohorts of 3. The first cohort will be given BCT intervention with a duration of 5 weeks. Subsequent cohorts will be given a BCT intervention duration (from 1-week to 10-week) based on the updated MED estimate according to the modified TiTE-CRM model and data from the previously enrolled participants. The process will continue until we reach a total of 42 participants (14 cohorts) randomized to the intervention; see sample size justification below.

All participants will then undergo 2 weeks of observation. In summary, participation will be between 5– 14 weeks depending on BCT dose assignment.

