## 16. WITHDRAWAL OF SUBJECTS

- *Describe anticipated circumstances under which subjects will be withdrawn from the research without their consent*
- *Describe procedures for orderly termination*
- *Describe procedures that will be followed when subjects withdraw from the research, including partial withdrawal from procedures with continued data collection.*

Circumstances under which participants will be withdrawn from the research without their consent include failure to maintain protocol adherence and repeated failure to complete the assigned BCT intervention.

Potential participants will be notified of the possibility of being removed from the study before or during the BCT intervention phase due to adherence issues in the informed consent. Participants who fail to maintain minimum adherence during baseline will be notified by the research team after 10 days of baseline participation.

Participants who fail to maintain protocol adherence or who deviate from the protocol will be contacted by a member of the study team with a reminder of the study protocol, and warning that this may impact their continued study eligibility. Once a protocol deviation has been repeatedly recorded, the Principal Investigator will determine the participant's continued eligibility in the study, with consultation of the Safety Officer if needed. If it is determined that the participant will be withdrawn from the study, the participant will be notified by the research team via email and phone call. The participant will stop receiving notifications and survey prompts, and will be sent instructions to un-link their Fitbit device. The participant will be able to keep their Fitbit device but will be required to return their eCAP smart pill bottle.

Participants may withdraw from participation in the research at any time. Given the non-invasive nature of study-specific monitoring, there are no significant anticipated direct adverse effects related to withdrawal. Participants may easily elect to withdraw by emailing Research personnel directly at:

[name]  
 [name]  
 [name]  
[[contact]](mailto:[contact])

If a participant withdraws from the study, previously collected data will not be deleted. However, no new information will be collected from a participant after he/she has withdrawn from the study. We will clarify how to transfer the Fitbit

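### The exploratory time-to-success analysis has no rule for participants who never succeed or who withdraw, and the time available to succeed varies with assigned duration

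*Combined protocol and SAP*

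**What the plan says.** Section 4 gives the exploratory aim as: "Identify between-person heterogeneity in Treatment Response". Section 12 makes this specific. The quantity of interest is "Participant heterogeneity in amount of time required to reach a successful increase in daily steps", where success is a gain of at least 2,000 steps per day over two weeks relative to run-in. The data steps are: "Average step counts will be calculated for each 2-week block during the intervention and follow-up periods"; each block is compared with run-in; and "Once a successful increase has been detected, the time to achieve this treatment response will be recorded". The resulting times are then compared from person to person by mixed effects regression.

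Two other sections determine what can be recorded. Section 9 says that "participation will be between 5– 14 weeks depending on BCT dose assignment", which includes the 2-week run-in and the 2-week follow-up. Section 16 says that "no new information will be collected from a participant after he/she has withdrawn from the study", and it lists among the grounds for withdrawal without consent "failure to maintain protocol adherence and repeated failure to complete the assigned BCT intervention".

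Section 12 also promises transparent reporting, so that differences between individuals can be seen. It sizes the study for the primary aim only.

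**The concern.** The stated steps produce a time only when a success is detected. Some participants will not have one. The primary target itself accepts up to 20% without success on the follow-up comparison at the chosen dose, although some of those may have succeeded in an earlier block. The plan names no censoring time, substitute value or survival method for them, or for people who withdraw first.

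The opportunity to succeed also differs by design. A participant assigned 1 week has far less time in which a success can be seen than one assigned 10 weeks. If the durations that exist are simply compared, the slowest people are missing, and the spread partly reflects how long each person was watched. The aim is differences between people in the time they need, so this affects the quantity being estimated. A later study planned from these times could expect success too early.

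**Working it through.** **Inputs from the documents.** Run-in 2 weeks; intervention d = 1 to 10 weeks; follow-up 2 weeks; two-week blocks; 14 cohorts of 3 = 42 participants.

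**Reproducing the plan's figure.** Total participation = 2 + d + 2. At d = 1 this is 5 weeks and at d = 10 it is 14 weeks, matching section 9.

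**Observation window.** Window after run-in = d + 2 weeks. Complete, non-overlapping blocks = floor(d/2) + 1, taking the follow-up as its own block. The plan does not state this grid, so it is an assumption.

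| d | Window (weeks) | Complete blocks K | Block ends (weeks) |
|---|---|---|---|
| 1 | 3 | 1 | 3 |
| 5 | 7 | 3 | 2, 4, 7 |
| 10 | 12 | 6 | 2, 4, 6, 8, 10, 12 |

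**Illustration.** Assume that every participant has the same chance p of first success in each block, at every duration, with p = 0.25 or 0.50. The documents give no such figure. There is then no true difference between people and no effect of duration.

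- Chance of first success in block k: p(1 − p)^(k−1).
- Share with no recorded time: (1 − p)^K.
- Mean and SD of recorded times: taken over the block ends, with the probabilities rescaled by 1 − (1 − p)^K.

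Example, d = 5, p = 0.25. The probabilities are 0.2500, 0.1875 and 0.1406, summing to 0.5781. Mean = (2 × 0.2500 + 4 × 0.1875 + 7 × 0.1406)/0.5781 = 3.86 weeks. Mean square = (4 × 0.2500 + 16 × 0.1875 + 49 × 0.1406)/0.5781 = 18.84, so SD = √(18.84 − 3.865²) = 1.98 weeks.

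| d | No time, p = 0.25 / 0.50 | Mean recorded time (weeks), p = 0.25 / 0.50 | SD (weeks), p = 0.25 / 0.50 |
|---|---|---|---|
| 1 | 75% / 50% | 3.00 / 3.00 | 0 / 0 |
| 5 | 42% / 12.5% | 3.86 / 3.29 | 1.98 / 1.75 |
| 10 | 18% / 1.6% | 5.40 / 3.81 | 3.17 / 2.38 |

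**Understatement.** If two-week blocks continued indefinitely at the same chance, the mean time would be 2/p: 8.0 weeks at p = 0.25 and 4.0 at p = 0.50. Even at d = 10 the recorded means are 5.40 and 3.81.

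**The grid matters too.** If blocks instead run continuously from the start of the intervention, K is unchanged, but the mean (SD) becomes 2.00 (0) at d = 1. At d = 5 it becomes 3.62 (1.60) for p = 0.25 and 3.14 (1.46) for p = 0.50. At d = 10 nothing changes. At d = 1, 3, 5, 7 and 9 one week is left over, and the plan does not say what happens to it.

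**A limit on any pooled curve.** With follow-up as its own block, the last block is off-intervention. Suppose, as a further assumption, that the chance of success halves there. At d = 6 the fourth block is follow-up, so success by block 4 is 1 − 0.75³ × 0.875 = 63%, against 1 − 0.75⁴ = 68% had the intervention continued. For p = 0.50 the figures are 1 − 0.5³ × 0.75 = 91% and 1 − 0.5⁴ = 94%.

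**The case against.** The strongest reply is that silence is not a plan to exclude. A reader might infer that non-responders will be dropped, but section 12 does not say so. It computes a step average in every block and names mixed models, so a block-level analysis of everyone is a possible reading. The promise of transparent individual reporting also makes it less likely that non-successes would go unseen in a study of this size. Both points stand as mitigation. Neither supplies a censoring rule, and the only quantity the section says will be compared is the duration to success.

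A reader might also infer that a mixed model cannot be fitted with one time per person. That presumes a participant random effect, and no random-effects structure is given; participants enter in cohorts of 3, so other groupings are possible. What can be said is that the structure is not stated.

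Third, the sizes rest on assumed success chances. That is correct. The direction does not: whenever some participants have not succeeded by the end of their window, recorded times alone run short. How many of the 42 would lack a time cannot be read from the documents, because it depends on the durations the adaptive design assigns and on success rates that are not given.

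**Conclusion.** The point holds as a minor, inexpensive improvement to one exploratory analysis. It is certain from the text that no rule covers participants who never succeed or who withdraw, and that the window runs from 3 to 12 weeks (1 to 6 complete blocks) according to assigned duration. It is conditional that, if only recorded times are analysed, time to success is understated and its spread depends partly on assignment. Under an equal 25% or 50% chance per block, with follow-up as its own block, mean recorded time is 3.0, 3.3 to 3.9 and 3.8 to 5.4 weeks at durations 1, 5 and 10, with no true difference between people.

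Two stronger readings are not supported. A reader might infer that the MED is compromised, but the primary analysis does not use these times; dose assignment, the MED and the 42 participants are unaffected. A reader might also infer that the plan would report a false effect of duration on speed of success, but it states no regression of time on assigned duration.

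**What to change.** In the Exploratory Aim paragraph of section 12:

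- Analyse time to first successful two-week block in all 42 participants as a discrete-time (grouped) outcome, right-censored at the end of follow-up or at withdrawal if earlier.
- Report Kaplan-Meier estimates and the number who never succeed.
- Because withdrawal can follow non-adherence, add a sensitivity analysis that keeps withdrawn participants as non-successes to their planned end.
- State the block grid, including the leftover week at odd durations, and the random-effects structure of any mixed model that is retained.
- Mark the off-intervention block as such, or show results by duration where numbers allow. Do not read the pooled curve as time to success under continued intervention.

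The cost is a few sentences and slightly more analysis work on the same Fitbit data, with no change to conduct. Intervals will be wide with 42 participants, and curves by duration may rest on very few people.
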